### **C 2 Definitions**

#### **Potential Hy's Law (PHL)**

Aspartate Aminotransferase (AST) or Alanine Aminotransferase (ALT)  $\geq 3 \times$  Upper Limit of Normal (ULN) together with Total Bilirubin (TBL)  $\geq 2 \times$  ULN at any point during the study following the start of study medication irrespective of an increase in Alkaline Phosphatase (ALP).

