## Hy's Law (HL)

AST or ALT  $\geq 3 \times \text{ULN}$  together with TBL  $\geq 2 \times \text{LN}$ , where no other reason, other than the IMP, can be found to explain the combination of increases, e.g., elevated ALP indicating cholestasis, viral hepatitis, another drug.

For PHL and HL the elevation in transaminases must precede or be coincident with (i.e. on the same day) the elevation in TBL, but there is no specified timeframe within which the elevations in transaminases and TBL must occur.

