4.6.3 Clinical Laboratory

4.6.3.1 Definition and Derivations

The parameters of haematology, serum chemistry, urinalysis and of fasting lipid profile (high density lipoprotein cholesterol, low density lipoprotein cholesterol, and triglycerides) are explored.

Laboratory data are reported in international system of units (SI). Changes from baseline in haematology, clinical chemistry, urinalysis and lipid profile variables are calculated.

Absolute values are compared to the reference range as given in Appendix 1.1 and classified as low (below range), normal (within range or on limits) or high (above range). All values (absolute and change) falling outside the reference ranges are flagged.

Treatment emergent laboratory changes (TELVC) are defined for post-baseline values according to the reference ranges given in Appendix 1.1.

Urinalysis data are categorized as negative (0), positive (+), or strongly positive (++, +++, or >+++)) at each time-point.

For the liver function tests: aspartate transaminase (AST), alanine transaminase (ALT), Alkaline phosphatase, gamma glutamyl transferase (GGT) and total bilirubin, the multiple of the upper limit of the normal (ULN) range (see Appendix 1.1) are calculated for each data point. Multiple = Value / ULN, i.e., if the ALT value was 72 IU/L (ULN = 36) then the multiple would be 2. Participants meeting both of the following biochemical criteria for Hy's law (potential Hy's Law) at any point during the study (not necessarily at the same time) are flagged:

- AST ≥ 3 x ULN and/or ALT ≥ 3 x ULN
- Total bilirubin ≥ 2 xULN

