4.6.3.2 Presentation

Observed values and changes from baseline of laboratory data for haematology, clinical chemistry, continuous urinalysis, and fasting lipid profile are summarized by visit. The summary statistics presented are minimum, 1st quartile, median, 3rd quartile, maximum, mean, and SD.

For each laboratory parameter with available criteria, the number and percentage of participants with TELVC values are summarized. Additionally, the number and percentage of participants with at least one TELVC value are presented. Percentages are based on participants with a measurement at baseline and at least 1 subsequent measurement of the variable.

The number and percentage of participants with laboratory values below, within or above the corresponding reference ranges are presented as shift tables from baseline to maximum and minimum on-treatment value, respectively.

Urinalysis is summarized as shift tables from baseline categorization to the last post-baseline value categorization for each parameter. Furthermore, the number and percentage of participants with treatment-emergent changes are summarized by parameter. Percentages for the summary of treatment emergent changes are based on participants with a measurement at baseline and at least 1 subsequent measurement of the variable. The three parameters Urine Glucose, Ketone Bodies and qualitative Erythrocytes should be added for presentation of TELVC for urinalysis. The criteria for TELVC for urinalysis data are defined as follows:

- Negative/positive at baseline to ++, +++, +++++ at any post-baseline value OR,
- Increase from baseline of at least ++ at any post-baseline value.

In order to identify potential Hy's Law cases, maximum on-treatment ALT and AST are summarized as number and percent versus maximum on-treatment total bilirubin.

All clinical safety laboratory data is listed, and any out-of-range laboratory measurements are flagged in the listing.

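### The SAP labels participants potential Hy's Law whichever rise came first, but the protocol requires the transaminase rise to come before, or on the same day as, the bilirubin rise

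*SAP*

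**What the plan says.** **Protocol, Appendix C 2.** Potential Hy's Law needs AST or ALT of at least 3×ULN together with total bilirubin of at least 2×ULN. Two conditions on timing apply. The values must arise "at any point during the study following the start of study medication". There is also an order rule: "For PHL and HL the elevation in transaminases must precede or be coincident with (i.e. on the same day) the elevation in TBL". On the interval between the two rises, Appendix C 2 adds that "there is no specified timeframe within which the elevations in transaminases and TBL must occur".

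**SAP 4.6.3.1.** The thresholds are the same: "AST ≥ 3 x ULN and/or ALT ≥ 3 x ULN" and "Total bilirubin ≥ 2 xULN". Participants meeting both "at any point during the study (not necessarily at the same time) are flagged". The SAP names this potential Hy's Law. It states no order and does not repeat the protocol's post-dose condition.

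**SAP 4.6.3.2.** For the stated purpose of identifying such cases, "maximum on-treatment ALT and AST are summarized as number and percent versus maximum on-treatment total bilirubin". Two maxima carry no information on which came first.

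**SAP 4.6.** Safety data are presented for treatment plus follow-up unless another period is given. On-treatment values run from after the first dose to 28 days after the last.

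SAP Section 2 records no departure from the protocol's planned analyses (it refers to protocol version 3.0).

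**The concern.** One defined term has two meanings in one trial. Investigators decide on potential Hy's Law, and report it as an SAE, under the ordered definition in Appendix C. The study report would use the same words for an unordered set and, as planned, would give no ordered count.

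The order rule removes a particular pattern: a bilirubin rise from another cause, followed later by a separate transaminase rise. That pattern is plausible here, because exclusion criterion 33(h) sets a lower haemoglobin limit where anaemia is SLE-related and gives active haemolysis as its example. What is at stake is how a rare and closely read liver output is interpreted. A participant could appear under a heading that the protocol's own definition would deny.

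**Working it through.** The documents give no rate or count of these cases, so there is no plan figure to reproduce. The check compares the rules on timing patterns.

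**Inputs**
- Limits: 3×ULN for AST or ALT, 2×ULN for bilirubin, identical in both documents.
- Study days from SAP Table 1: Week 8 = 57, Week 12 = 85, Week 48 (last dose) = 337, Week 56 = 393.
- End of the on-treatment window for a completer: 337 + 28 = Day 365.
- First follow-up visit, 8 weeks after the last dose, with serum chemistry scheduled (Protocol Table 5): 337 + 56 = Day 393.
- Day −10 is an illustrative pre-dose day.

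**Rules applied** (T = day AST or ALT reaches its limit, B = day bilirubin reaches its limit, each rise occurring once)
- Protocol C 2: T and B both after first dose, and T ≤ B.
- SAP flag, literal wording: T and B both exist, at any time.
- SAP flag under the 4.6 default period: T and B both after first dose.
- SAP 4.6.3.2 table: T and B both after first dose and no later than Day 365.

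| Pattern | T | B | Protocol C 2 | SAP flag, literal | SAP flag, 4.6 default | SAP table |
|---|---|---|---|---|---|---|
| Transaminase first | 57 | 85 | yes | yes | yes | yes |
| Same day | 57 | 57 | yes | yes | yes | yes |
| Bilirubin first | 85 | 57 | **no** | **yes** | **yes** | **yes** |
| Bilirubin pre-dose only | 57 | −10 | no | yes | no | no |
| Transaminase pre-dose only | −10 | 57 | no | yes | no | no |
| Both pre-dose | −10 | −10 | no | yes | no | no |
| Transaminase on treatment, bilirubin in follow-up | 337 | 393 | yes | yes | yes | **no** |

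**Reading the table** (these are patterns, not frequencies)
1. The bilirubin-first row differs from the protocol under every SAP rule. This conflict depends on no choice of reading.
2. The three pre-dose rows differ only under the literal flag wording. They disappear if the 4.6 default governs, and they never reach the table.
3. Every protocol case is caught by the flag under either reading, so the flag is a superset.
4. The on-treatment table stops before the follow-up visits. It can omit a protocol case completed there, which the flag would catch.
5. The SAP's allowance for rises at different times is not a conflict, because Appendix C 2 sets no maximum gap.

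**The case against.** The strongest reply is that the SAP output is a screen, not a case decision. It speaks of biochemical criteria. Under Appendix C the investigator determines whether the definition is met, and the sponsor then reviews it. The protocol's own identification step (C 3) is unordered and is triggered by any single limit, and Protocol 6.4.8 gives the limits without an order. Screens normally err towards inclusion. Protocol Table 6 requires the liver tests to be run and assessed together, so both limits may often be met on one draw. All safety laboratory data are listed, so the order can be checked case by case. No efficacy result and no participant-level safety action depends on the SAP flag.

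Most of that stands, and it limits the consequence. It does not remove the mismatch. C 3 triggers a review and C 2 is the definition; 6.4.8 refers to Appendix C. The SAP does not call its output a screen. It uses the protocol's term, gives case identification as the purpose of the table, and provides no ordered count beside it.

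A reader might infer more than the documents support:
- **That pre-dose values are counted.** The flag wording does not expressly exclude them, but the 4.6 default period arguably does and the table certainly does. Exclusion criterion 33 also bars AST or ALT above 2×ULN at screening, so a qualifying pre-dose transaminase value should be uncommon.
- **That the flag could hide a case.** It cannot, since it is a superset of the protocol definition in the laboratory data analysed.
- **That this wording alone makes the report disagree with the SAE counts.** Those could differ even after correction. Appendix C lets local laboratory results count, revises the SAE term when another explanation is agreed, and generally asks for no SAE where the criteria were already met before dosing.
- **That some fixed share, such as half, of flagged participants are non-cases.** That needs an assumed random order of unrelated rises, which nothing in the documents supports.

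**Conclusion.** The point holds as a mismatch of definitions. SAP 4.6.3.1 and 4.6.3.2 label a bilirubin-first participant potential Hy's Law, and Protocol Appendix C 2 says that participant is not a case. A secondary gap is that the flag wording is silent on pre-dose values, with the limits given above.

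The error is one of over-inclusion in the flag. Its size cannot be derived: it is nil if every qualifying pair is same-day or transaminase-first, and otherwise it equals the number of participants whose only qualifying pairs have bilirubin first. The consequence is confined to the labelling and interpretation of a descriptive safety output.

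The conclusion assumes that a bilirubin-first participant has no bilirubin value at or above the limit on or after the day of the transaminase rise. Appendix C 2 does not say whether order is judged on first crossings or on any qualifying pair. The indicator proposed below uses any qualifying pair, so a bilirubin rise that persists through the transaminase rise would count.

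**What to change.** In SAP 4.6.3.1, add a derived indicator that matches Appendix C 2: AST or ALT of at least 3×ULN after the first dose, with total bilirubin of at least 2×ULN on the same or a later date, using values through the end of follow-up. State that any qualifying pair is enough, and report the indicator by arm.

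Keep the unordered flag and the maximum-by-maximum table. Label both as a broad biochemical screen, mark the participants who meet the ordered definition, and footnote that the table covers on-treatment values only.

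The cost is a few sentences in the SAP, one date comparison in the program and a footnote. The data are already collected and listed, and no planned output is lost.

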4.6.3.2 Presentation

Observed values and changes from baseline of laboratory data for haematology, clinical chemistry, continuous urinalysis, and fasting lipid profile are summarized by visit. The summary statistics presented are minimum, 1st quartile, median, 3rd quartile, maximum, mean, and SD.

For each laboratory parameter with available criteria, the number and percentage of participants with TELVC values are summarized. Additionally, the number and percentage of participants with at least one TELVC value are presented. Percentages are based on participants with a measurement at baseline and at least 1 subsequent measurement of the variable.

The number and percentage of participants with laboratory values below, within or above the corresponding reference ranges are presented as shift tables from baseline to maximum and minimum on-treatment value, respectively.

Urinalysis is summarized as shift tables from baseline categorization to the last post-baseline value categorization for each parameter. Furthermore, the number and percentage of participants with treatment-emergent changes are summarized by parameter. Percentages for the summary of treatment emergent changes are based on participants with a measurement at baseline and at least 1 subsequent measurement of the variable. The three parameters Urine Glucose, Ketone Bodies and qualitative Erythrocytes should be added for presentation of TELVC for urinalysis. The criteria for TELVC for urinalysis data are defined as follows:

- Negative/positive at baseline to ++, +++, +++++ at any post-baseline value OR,
- Increase from baseline of at least ++ at any post-baseline value.

In order to identify potential Hy's Law cases, maximum on-treatment ALT and AST are summarized as number and percent versus maximum on-treatment total bilirubin.

All clinical safety laboratory data is listed, and any out-of-range laboratory measurements are flagged in the listing.

4.6.4 Electrocardiogram (ECGs)

4.6.4.1 Definition and Derivations

12-lead ECGs for all participants at all centers are conducted at the centers using standardized ECG machines throughout the study. The Investigator judges the overall interpretation as normal or abnormal. If abnormal, it is decided as to whether the abnormality is clinically significant or not clinically significant and the reason for the abnormality are recorded on the eCRF, if the Investigator considers it clinically significant. The following categories are used for analysis:

- Normal,
- Abnormal, not clinically significant,
- Abnormal, clinically significant.

In case of repeated measurements (triplicates) at a visit, the worst category at the respective visit will be used for the analysis.

4.6.4.2 Presentation

The number and percentage of participants with normal, abnormal, not clinically significant, and abnormal, clinically significant ECG results are presented as a shift table from baseline to last observation.

4.6.5 Vital signs

4.6.5.1 Definition and Derivations

The following variables will be explored:

- Pulse (beats per minute)
- Systolic blood pressure (mmHg)
- Diastolic blood pressure (mmHg)
- Respiration rate (breaths per minute)
- Body temperature (°C)
- Body weight (kg)

Changes from baseline will be calculated.

Where applicable, absolute values are compared to the reference ranges given in Appendix 7.3 and classified as low (below range), normal (within range or on limits) or high (above range). All values (absolute and change) falling outside the reference ranges will be flagged.

Post-baseline values are classified as TELVC according to reference ranges given in Appendix 7.3.

For infusion visits, only measurements before start of IP are considered for by visit presentations. In case of multiple measurements before the start of IP, the first measurement is used for by visit presentations, but all measurements will be considered for the TELVC classification.

4.6.5.2 Presentation

Observed values and changes from baseline of pulse, systolic blood pressure (SBP), diastolic blood pressure (DBP), respiration rate, body temperature, and body weight, respectively, are summarized by visit. The summary statistics presented are minimum, 1st quartile, median, 3rd quartile, maximum, mean, and SD.

For each parameter with available criteria, the number and percentage of participants with TELVC values are summarized. Percentages are based on participants with a measurement at baseline and at least 1 subsequent measurement of the variable.

For pulse, SBP and DBP, the number and percentage of participants with values below, within or above the corresponding normal range is presented as shift tables from baseline to maximum and minimum on-treatment value, respectively.

4.6.6 C-SSRS

4.6.6.1 Definition and Derivations

The C-SSRS is an assessment tool that evaluates suicidal ideation and behavior.

Two different versions of the questionnaire were used:

- Baseline/Screening version, assessing the last 12 months prior to the assessment
- Since Last Visit Version, assessing the time since last visit.

The following outcomes are C-SSRS categories and have binary responses (yes/no). The categories have been re-ordered from the actual scale in an increasing order of severity from 1 to 10 to facilitate the definitions of the comparative variables.

- Category 1 – Wish to be Dead
- Category 2 – Non-specific Active Suicidal Thoughts
- Category 3 – Active Suicidal Ideation with Any Methods (Not Plan) without Intent to Act
- Category 4 – Active Suicidal Ideation with Some Intent to Act, without Specific Plan
- Category 5 – Active Suicidal Ideation with Specific Plan and Intent
- Category 6 – Preparatory Acts or Behavior
- Category 7 – Aborted Attempt
- Category 8 – Interrupted Attempt
- Category 9 – Actual Attempt (non-fatal)

- Category 10 – Completed Suicide

Composite variables based on the above re-ordered categories are defined for assessments during screening, during treatment and follow-up period, respectively as follows:

- Suicidal ideation: A “yes” answer at any time in the respective study period to any one of the 5 (re-ordered) suicidal ideation questions (Categories 1-5) on the C-SSRS.
- Suicidal behavior: A “yes” answer at any time in the respective study period, to any one of the 5 (re-ordered) suicidal behavior questions (Categories 6-10) on the C-SSRS.
- No suicidal ideation or behavior: No “yes” answer at any time in the respective study period to any one of the 10 (re-ordered) suicidal ideation and behavior questions (Categories 1-10) on the C-SSRS.

The total number of attempts, total number of interrupted attempts, and total number of aborted attempts will be derived for the different study periods by summing up all respective attempts during screening, during treatment and follow-up period, respectively.

For summary of C-SSRS data, the following period definitions will be used:

- Screening Period:
Assessments with a date \geq date of first screening visit (S1) and \leq date of the first dose of IP.
- During treatment and follow-up period:
Assessments with a date $>$ date of first dose of IP and \leq date of last dose of IP + 84 days.

If the wrong questionnaire version (Baseline/Screening rather than since last visit or vice versa) was used for an assessment, the assessment will be assigned to a period based on assessment date, regardless of the version that was completed.

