#### Medical Conditions

1. History of, or current diagnosis of, a clinically significant non-SLE related vasculitis syndrome (see [Appendix J](#)). Vasculitis due to SLE is allowed in the study.
2. History or evidence of suicidal ideation (severity of 4 [active: method and intent, but no plan] or 5 [active: method, intent, and plan]) within the past 6 months; or any suicidal behavior within the past 12 months or recurrent suicidal behaviour in the lifetime of the participant based on an assessment with the C-SSRS ([Appendix Q](#)) at screening or at baseline.
3. Active severe or unstable neuropsychiatric SLE including, but not limited to aseptic meningitis; cerebral vasculitis; myelopathy; demyelination syndromes (ascending, transverse, acute inflammatory demyelinating polyradiculopathy); acute confusional state; impaired level of consciousness; psychosis; acute stroke or stroke syndrome; cranial neuropathy; status epilepticus; cerebellar ataxia; and mononeuritis multiplex:
  - (a) Where, in the opinion of the Principal Investigator (PI), delegated Sub-Investigator (SI) or Sponsor, protocol specified standard therapy is insufficient and utilization of a more aggressive therapeutic approach, such as adding IV cyclophosphamide and/or high dose IV pulse corticosteroid therapy or other treatments not permitted in the protocol, is indicated.
4. Active severe SLE-driven renal disease where, in the opinion of the PI or delegated SI or Sponsor, protocol specified standard therapy is insufficient and utilization of a more aggressive therapeutic approach, such as adding IV cyclophosphamide and/or high dose IV pulse corticosteroid therapy or other treatments not permitted in the protocol, is indicated.
5. Diagnosis (within 1 year of signing the ICF) of mixed connective tissue disease or any history of overlap syndromes of SLE and systemic sclerosis (SSc), as noted in (a) or (b) below:
  - (a) An overlap syndrome of SLE with myositis or rheumatoid arthritis at Screening is permitted provided the participant also meets the criteria for the classification as SLE; or
  - (b) A history of mixed connective tissue disease, which over time has developed into a diagnosis of SLE, is permitted provided diagnosis of SLE has been present for at least 1 year.

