### **5.2.5 Columbia Suicide Severity Rating Scale**

The C-SSRS (Appendix Q) is a unique, simple, and short method of assessing both behaviour and ideation that tracks all suicidal events, and provides a summary of suicidality (Posner et al, 2007). It assesses the lethality of attempts and other features of ideation (frequency, duration, controllability, reasons for ideation, and deterrents), all of which are significantly predictive of completed suicide.

The C-SSRS will be administered at all study visits by a trained rater. The trained rater will record the clinical observation on the scale, which will be used as the source document. If at all possible, the same individual should perform the assessment at each visit to reduce scoring variability. In the event the primary rater is not available, a designated back-up rater who meets the same qualifications may perform the C-SSRS. An Investigator physician will review completed C-SSRS responses on the day of assessment and document review within the source.

If a participant indicates having a rating of type 4 or 5 suicidal ideation on the C-SSRS suicidal ideation scale at any time since the previous visit when the C-SSRS was administered or indicates having had any suicidal behaviour since the previous visit, the participant should be referred to a mental health professional immediately. If the C-SSRS is administered by a

rater other than the Primary Investigator, it is recommended that the Primary Investigator confirms suicidal ideation before making a referral to mental health services; however this should not delay the referral.

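### Wrong-version C-SSRS forms are assigned by assessment date alone, so a 12-month-recall form completed after first dose can count pre-dose suicidal ideation in the treatment and follow-up period

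*SAP*

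**What the plan says.** SAP 4.6.6.1 describes two forms with different recall: "Baseline/Screening version, assessing the last 12 months prior to the assessment" and "Since Last Visit Version, assessing the time since last visit". A participant has suicidal ideation in a period after a yes "answer at any time in the respective study period to any one of the 5 (re-ordered) suicidal ideation questions". The behaviour composite has the same structure.

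The screening period takes assessments up to and including the first-dose date. The treatment and follow-up period takes later ones up to the "date of last dose of IP + 84 days". For a form of the wrong version, "the assessment will be assigned to a period based on assessment date, regardless of the version that was completed". SAP 4.6.6.2 then tabulates ideation and behaviour by maximum category, with attempt totals, for each period.

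The C-SSRS section has no flag, query, separate listing or sensitivity analysis for these forms. The data-exclusion section (SAP 3.3.9) covers only the EQ-5D-5L.

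On the protocol side, section 5.2.5 states: "The C-SSRS will be administered at all study visits by a trained rater". Exclusion criterion 2 removes ideation with "severity of 4 [active: method and intent, but no plan] or 5 [active: method, intent, and plan]) within the past 6 months" and also any suicidal behaviour in the past 12 months, or recurrent behaviour over the lifetime, assessed at screening or at baseline.

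**The concern.** The rule fixes the date of the form but not the date of the event. A correct Since Last Visit form at Week 4 asks about the time since Day 1. A Baseline/Screening form completed at the same visit asks mostly about time before the first dose. Because any yes makes the participant a case for the period in which the form falls, earlier ideation would be reported under treatment and follow-up. Protocol 8.4.6 describes the measure as occurrence from baseline to Week 52, so such a count measures something else.

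This is a stated rule that can give a wrong safety count, not merely a missing detail. False cases in either arm blur the between-arm comparison, and false placebo cases can hide a real difference, so over-counting is not automatically the cautious choice. In the other direction, a Since Last Visit form used at the screening visit does not cover the 12-month history and can understate the screening row.

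**Working it through.** The documents give no event count or error rate for the C-SSRS, so there is no figure of the plan's own to reproduce. The check is a day count set against the eligibility criteria.

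**Inputs.** Scheduled study day *d* for each visit (SAP 3.3.2, Table 1: Week 4 = Day 29 through Week 60 = Day 421). Look-back of 12 months, taken as 365 days (SAP 4.6.6.1). Exclusion windows from Protocol 3.2, criterion 2: type 4-5 ideation over 6 months, taken as 182 days, and any behaviour over 12 months. Screening lasts up to 35 days (Protocol 1.4).

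**Step 1: share of the look-back before first dose.** Pre-dose days = max(0, 365 − (*d* − 1)). This share applies to type 1-3 ideation, which criterion 2 does not exclude.

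**Step 2: days that could still hold type 4-5 ideation.** If the 6 months are counted back from Day 1, this is max(0, pre-dose days − 182). If they are counted from a screening visit 35 days earlier, with the interval up to Day 1 covered by the baseline assessment, it is max(0, pre-dose days − 182 − 35).

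| Visit | Day | Pre-dose days of 365 | Type 4-5 possible, from Day 1 | Type 4-5 possible, from screening |
|---|---|---|---|---|
| Week 4 | 29 | 337 (92%) | 155 (42%) | 120 (33%) |
| Week 8 | 57 | 309 (85%) | 127 (35%) | 92 (25%) |
| Week 12 | 85 | 281 (77%) | 99 (27%) | 64 (18%) |
| Week 24 | 169 | 197 (54%) | 15 (4%) | 0 |
| Week 36 | 253 | 113 (31%) | 0 | 0 |
| Week 48 | 337 | 29 (8%) | 0 | 0 |
| Week 52 | 365 | 1 (0.3%) | 0 | 0 |
| Weeks 56, 60 | 393, 421 | 0 | 0 | 0 |

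**Step 3: an example that eligibility permits.** Take type 5 ideation 8 months (about 243 days) before screening, with the full 35-day screening period. It lies 243 + 35 + 28 = 306 days back at Week 4, 334 at Week 8 and 362 at Week 12, all inside the look-back. At Week 16 it is 390 days back and outside. A Baseline/Screening form completed at Week 4, 8 or 12 could therefore report it as category 5 during treatment and follow-up.

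**Step 4: behaviour and attempts.** After first dose, a 12-month look-back reaches less than 12 months before first dose. Criterion 2 already removes anyone with suicidal behaviour "within the past 6 months; or any suicidal behavior within the past 12 months", so an eligible participant has essentially none to carry forward. The exception is the Lifetime column that the Baseline/Screening form in Protocol Appendix Q also carries. A single attempt more than 12 months old is not excluded, and the SAP does not say which column feeds the analysis. Using that column would also remove the Week 52 limit for ideation.

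**Step 5: illustration of size.** These values are assumptions, not figures from the documents: 1 to 10 wrong-version forms per arm, in different participants, and 2% to 10% of participants with pre-study ideation in the window. Expected false cases per arm = forms × prevalence, from 1 × 0.02 = 0.02 to 10 × 0.10 = 1.0. With 130 per arm that is 0.02 to 0.8 percentage points.

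**The case against.** The strongest reply is that the rule is a contingency for a rare error in a descriptive table. Protocol 5.2.5 requires a trained rater and same-day physician review. The form has description fields and attempt dates, so misdated answers can be clarified at source. Blinding should make mix-ups similar in both arms. The SAP heads the period treatment and follow-up, shows screening alongside it, and does not claim onset on drug. Keeping every reported yes is also a defensible default for safety data.

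Most of this stands, and it limits the size. It does not remove the error: the review confirms the responses, but the SAP rule then counts them by form date whatever the review finds.

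A reader might infer that on-treatment behaviour and attempt totals are inflated too, or that the 92% share at Week 4 applies to severe ideation. Criterion 2 contradicts both, as steps 2 and 4 show. A reader might also conclude that every post-dose Baseline/Screening form should be set aside. That would discard valid information, because a no over 12 months includes a no since the last visit. It would also drop an undated yes at Week 48, where only 8% of the window is pre-dose. Nor should Since Last Visit forms completed on or before Day 1 be removed. The C-SSRS is scheduled at both screening and Week 0, and the documents do not say which version belongs on Day 1, so some of those forms may be correct.

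**Conclusion.** The point holds in a limited form. A Baseline/Screening form completed after first dose and before about Week 52 can count pre-dose ideation in the treatment and follow-up summary. This mainly concerns type 1-3 ideation. Type 4-5 ideation more than 6 months old can be affected at early visits, to about Week 24 at most. Behaviour and attempts are essentially unaffected under 12-month recall.

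The conclusion assumes that exclusion criterion 2 is applied as written and that the Lifetime column is not used. The number of wrong-version forms is unknown. The effect is probably small and non-differential, and nothing in the documents shows that it would change a safety conclusion or favour either arm. It is worth correcting because the rule is explicit and the repair is cheap.

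**What to change.** Amend SAP 4.6.6.1 as follows:

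- Keep assignment by assessment date, and keep all no answers and all undated yes answers.
- Do not count in the treatment and follow-up summary a yes on a post-dose Baseline/Screening form when the form's description, its dates or a blinded query shows that the event occurred only before first dose.
- Flag and list every wrong-version form, and show the summary with and without undated yes answers from those forms.
- State that the Lifetime column is not used for the treatment and follow-up period.
- Flag a Since Last Visit form used at the screening visit as not covering the 12-month history. Leave Since Last Visit forms completed on Day 1 in the screening-period record.

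The cost is a change of SAP wording, a blinded review of what should be a few forms, and one extra display. Protocol 8.1 requires the final SAP amendment before unblinding, so the review should be finished by then.
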